4.4 Discussion Regarding ‘Event-Free Days’

Outcomes like duration of mechanical ventilation and incidence of organ failure may be lower in the group with higher mortality simply because of the competing effect of mortality (Rubenfeld, Angus et al 1999)³. Patients who die are not at risk to develop further organ failures or prolonged ventilator dependence. One proposed solution to this problem is to calculate life-support-free days. For example, ventilator-free days can be calculated over a predefined measurement period of (typically) 28 days. Patients who die or are mechanically ventilated longer than this period are assigned zero ventilator-free days for any days on which the patient is not alive or any day beyond the 28 days. All survivors accrue one ventilator-free day for each day after entry into the study that they are both alive and free of mechanical ventilation. By combining mortality and morbidity in one measure, the

³ Rubenfeld, GD, Angus DC, et al. Outcomes reserach in critical care. Am J Respir Crit Care Med 1999, 160(358-367).

“free-day” outcome avoids the problem of competing mortality. A similar approach will be used to determine ICU-free days and vasopressors-free days.

The 28-day horizon will be used when determining ICU-free days, vasopressor-free days, and mechanical ventilation-free days. ICU time will be calculated using calendar days starting on the day of admission to the ICU and ending on the day of ICU discharge, inclusive.

A vasopressor-free day or ventilator-free day will be defined based on calendar days starting from the day of drug administration. Any day upon which a patient experienced no part of a calendar day on a vasopressor or a ventilator is a ventilator/vasopressors-free day. For example, if the patient was on a ventilator for one hour on any given day, or for even one minute, this day will not count as a ventilator-free day. The same method will be used in calculating vasopressor-free days; a vasopressor-free day means a day alive and not on a vasopressor at any time during that day. This method is a convention generally accepted for these parameters. Events that occur under general anesthesia are not counted. Hospital length of stay will be calculated according the total number of calendar days in the hospital. Where indicated as such in the patient’s medical record the hospital discharge date will be recorded as the date when the hospital staff indicate that the patient is ‘ready for discharge’ (to avoid extending hospital length of stay solely because the patient is waiting to be placed in skilled nursing facility or equivalent setting but had recovered adequately from their illness to meet hospital discharge criteria).

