8.3 Secondary and Exploratory AKI Recovery Endpoints

Table 14.2.2.1 summarizes treatment group comparisons based on secondary AKI recovery endpoints in the mITT analysis set including:

- Freedom from durable loss of renal function at Day 14
- Freedom from durable loss of renal function at Day 90
- Improvement or freedom from durable loss at Day 14
- Improvement or freedom from durable loss at Day 28
- Improvement or freedom from durable loss at Day 90

Tables 14.2.2.2 and 14.2.2.3 repeat these comparisons in the AT and PP analysis sets, respectively.

8.4 mSOFA Scores

Table 14.2.4.1 summarizes observed modified total score, organ specific scores, and mSOFA total scores at Screening, Day 1, Day 3, Day 7, and Day 14.

Table 14.2.4.2 provides the same summary after application of last-value-carried forward (LOCF). LOCF was not applied after patient death.

Table 14.2.4.3 summarizes mSOFA at Screening and changes from Screening to Day 1, Day 7, and Day 14 for observed cases.

Table 14.2.4.4 provides the same summary after application of LOCF.

Table 14.2.4.5 summarizes the percentages of subjects with resolution of organ dysfunction (organ resolution is defined as having a total mSOFA score of ≤ 1) at day 14 and the resolution of specific organ dysfunction defined as having an individual organ SOFA score of ≤ 1 at Day 14.

8.5 Critical Care and Hospital Stay Parameters, to be Measured until Day 28

The following critical care and hospital stay parameters will be assessed.

- Hospital length of stay (days)
- ICU free days
- Days in ICU
- Days on ventilator
- Ventilator free days
- Vasopressors days
- Vasopressors free days
- Discharge status

Because of the expected skewness in the distributions of these parameters, non-parametric Wilcoxon rank sum tests will be used to assess the nominal statistical significance of treatment group differences in these parameters. Table 14.2.5.1 will provide summary statistics by treatment groups including N, mean, median, standard deviation, and minimum, and maximum values.

Table 14.2.5.2 summarizes hospital discharge status.

Table 14.2.5.3 summarizes hospital readmissions.

Table 14.2.5.4 will summarize critical care and hospital stay parameters over days 1 to 28 comparing by primary effectiveness status (success versus failure).

Table 14.2.5.5 will summarize critical care and hospital stay parameters over days 1 to 28 comparing subjects with Day 14 mSOFA ≤ 1 versus Day 14 mSOFA ≥ 2 .

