32	14.2.1.4	Site Variability in Primary Efficacy Endpoint in the mITT Analysis Set
33	14.2.2.1	Numbers and Percentages of Subjects Achieving Secondary Freedom from or Improvement in Durable Loss of Renal Function Endpoints at Days 14, 28, and 90 mITT Analysis Set
34	14.2.2.2	Numbers and Percentages of Subjects Achieving Secondary Freedom from or Improvement in Durable Loss of Renal Function Endpoints at Days 14, 28, and 90 AT (Safety) Analysis Set
36	14.2.2.3	Numbers and Percentages of Subjects Achieving Secondary Freedom from or Improvement in Durable Loss of Renal Function Endpoints at Days 14, 28, and 90 Per Protocol Analysis Set

		SOFA
37	14.2.4.1	Modified SOFA Total Score, Organ Specific Scores, and SOFA Total Score At Screening, Day 1, Day 3, Day 7, and Day 14 By Treatment Group Observed Cases mITT Analysis Set
38	14.2.4.2	Modified SOFA Total Score and Organ Specific Scores Over Time to Day 14 By Treatment Group Last Observation Carried Forward (LOCF) By Treatment Group mITT Analysis Set†
39	14.2.4.3	Modified SOFA Total Score, Organ Specific Scores, and SOFA Total Score At Screening and Changes from Screening to Day 1, Day 3, Day 7, and Day 14 By Treatment Group Observed Cases mITT Analysis Set†
40	14.2.4.4	Modified SOFA Total Score, Organ Specific Scores, and SOFA Total Score At Screening and Changes from Screening to Day 1, Day 3, Day 7, and Day 14 By Treatment Group Last Observation Carried Forward (LOCF) mITT Analysis Set†
41	14.2.4.5	Resolution of Organ Dysfunction to Days 14 Overall and by Individual Organ By Treatment Group mITT Analysis Set
42	14.2.4.6	Resolution of Organ Dysfunction to Days 14 Overall and by Individual Organ By Treatment Group mITT Analysis Set Among Subjects Presenting with Shock
43	14.2.4.7	Resolution of Organ Dysfunction to Days 14 Overall and by Individual Organ By Treatment Group PP Analysis Set
44	14.2.4.8	Resolution of Organ Dysfunction to Days 14 Overall and by Individual Organ By Treatment Group PP Analysis Set Among Subjects Presenting with Shock

Critical Care		
45	14.2.5.1	Critical Care and Hospital Stay Parameters Over Days 1 to 28 By Treatment Group mITT Analysis Set†
46	14.2.5.2	Hospital Discharge Status By Treatment Group mITT Analysis Set
47	14.2.5.3	Hospital Readmissions By Treatment Group mITT Analysis Set
48	14.2.5.4	Critical Care and Hospital Stay Parameters Over Days 1 to 28 By Primary Effectiveness Endpoint* Success vs. Failure mITT Analysis Set

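### ICU time is counted from ICU admission and hospital stay as the whole stay, although the output tables cover Days 1 to 28 from dosing, so pre-dose days can enter two secondary endpoints

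*SAP*

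**What the plan says.** ICU and hospital length of stay are secondary endpoints (Protocol 5.2 and 12.2, SAP 4.2). The counting rules are in SAP 4.4:

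- **ICU time:** "ICU time will be calculated using calendar days starting on the day of admission to the ICU", running through the day of ICU discharge inclusive.
- **Hospital stay:** "Hospital length of stay will be calculated according the total number of calendar days in the hospital". No start day is named. The text that follows adjusts only the discharge end.
- **Ventilator-free and vasopressor-free days:** "A vasopressor-free day or ventilator-free day will be defined based on calendar days starting from the day of drug administration". Plain ventilator days and vasopressor days have no stated start.
- **Free days in general:** "All survivors accrue one ventilator-free day for each day after entry into the study" on which they are alive and off the ventilator, and "A similar approach will be used to determine ICU-free days and vasopressors-free days". The horizon is given as "The 28-day horizon will be used when determining ICU-free days, vasopressor-free days, and mechanical ventilation-free days".

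The reporting window is set elsewhere. SAP 8.5 is headed "Critical Care and Hospital Stay Parameters, to be Measured until Day 28", and its text describes two of the comparisons as covering days 1 to 28. Table 14.2.5.1 in SAP Appendix 1 is titled "Critical Care and Hospital Stay Parameters Over Days 1 to 28 By Treatment Group". The protocol synopsis (study visits table) and Protocol 7.3 (Visit 2) start Day 1 at study drug administration and end it with that calendar day.

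**The concern.** For a patient already in the ICU or hospital on a calendar day before dosing, the counting rule includes that day and the table title excludes it. The SAP does not say which governs, so the choice would fall to the programmer.

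The design makes such patients likely. Current ICU admission qualifies for entry (inclusion criterion 4). Acute kidney injury (AKI) may be diagnosed up to 48 hours after the infection, with a further 6-hour dosing window (criteria 5 and 6). Transfer after a procedure at an outside hospital is allowed (Protocol 7.3, Visit 2). The reference-creatinine rule also foresees patients admitted without an acute illness, whose infection then begins in hospital.

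Days before dosing are fixed before treatment can act. Counting them adds variance to endpoints compared by a Wilcoxon test and makes a real difference harder to see. It also leaves ICU stay on a different clock from ventilator-free and vasopressor-free days.

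**Working it through.** The documents state no mean, SD or power for ICU or hospital days, so there is no figure to reproduce. The check is day counting, followed by an illustration under assumptions.

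**1. Length of the pre-dose period.** From infection diagnosis to dosing in late-AKI patients: 48 h + 6 h = 54 h, which spans about 0 to 3 earlier calendar days. Measured from hospital admission there is no upper limit for hospital-onset or transferred patients.

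**2. Effect on one patient.** Take a survivor with k pre-dose ICU calendar days who leaves the ICU on Day 8.

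| k | ICU stay from dosing (8) | ICU stay from admission (8 + k) | ICU-free over Days 1-28 (28 − 8) | ICU-free as 28 − ICU time |
|---|---|---|---|---|
| 0 | 8 | 8 | 20 | 20 |
| 1 | 8 | 9 | 20 | 19 |
| 2 | 8 | 10 | 20 | 18 |
| 3 | 8 | 11 | 20 | 17 |
| 7 | 8 | 15 | 20 | 13 |

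The post-dose course is the same in every row. The last column applies only if ICU-free days are programmed by subtraction, which the SAP does not state.

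**3. Effect on power.** Simulation with 60 patients per arm, a two-sided 0.05 Wilcoxon test and lognormal post-dose days. Every distribution, ratio and share below is an assumption.

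*ICU stay, log-SD 0.8, treated median 0.65 times control, 0-3 pre-dose days:*

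| Control median (days) | Power from dosing | Power from admission |
|---|---|---|
| 5 | 0.815 | 0.756 |
| 7 | 0.813 | 0.775 |
| 8 (capped at 28) | 0.817 | 0.790 |

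A separate run at median 5 with a cap at 28 days gave 81% against 74%. In the median-8 case, if 25% of patients also have extra pre-dose days with mean 7, power is 0.803 against 0.646, a loss of about 16 points.

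*Hospital stay, control median 13, log-SD 0.6, ratio 0.72, post-dose days capped at 28. A given share of patients has 3-14 pre-dose days and the rest 0-2:*

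| Share with 3-14 pre-dose days | Power from dosing | Power from admission |
|---|---|---|
| 0% | 0.83 | 0.82 |
| 5% | 0.81 | 0.79 |
| 10% | 0.81 | 0.76 |
| 25% | 0.82 | 0.71 |

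With 4,000 trials the simulation standard error of one power estimate near 0.8 is √(0.8 × 0.2 / 4000) ≈ 0.006, so the loss in the 0% row is close to simulation error.

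**4. Type I error.** With no treatment effect and counting from admission, the median-8 ICU setting rejects in 0.054 of trials (0-3 pre-dose days) and 0.046 (with the 25% long-stay group). There is no inflation.

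**The case against.** The strongest reply is that the window is already set. The tables are limited to Days 1 to 28, Day 1 is the dosing day, and the ICU sentence could be read only as a rule to count admission and discharge days inclusively within that window. That reading is possible, but the sentence names the day of ICU admission as the start without qualification, and the heading of SAP 8.5 gives only an end. The conflict stands as one of wording to be resolved.

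Total stay is also a legitimate measure, and Protocol 10.3 wants length of stay for health economics. That stands, and is a reason to keep total stay as a listing. Patients whose ICU admission is only planned at entry may have no pre-dose ICU days at all.

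A reader might infer four stronger points that the documents do not support:

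- **That pre-dose days are built into ICU-free days.** SAP 4.4 ties free days to days after study entry and applies a similar approach to the ICU. The problem arises only if the programmer computes 28 minus ICU time.
- **That ventilator and vasopressor days start at dosing.** The dosing start is stated only for the free-day versions.
- **That imbalance in AKI acuity biases the comparison.** Pre-dose stay is fixed before dosing and balanced in expectation. Acuity is a stratification factor (Protocol 12.6.1, SAP 2.2).
- **That a power loss of 10 points or more is to be expected.** It depends on about 25% of patients having long pre-dose stays, a share found in neither document.

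**Conclusion.** The concern holds as an unresolved conflict between the counting rules in SAP 4.4 and the Days 1 to 28 window in SAP 8.5 and Appendix 1. The admission start is explicit for ICU time. For hospital stay it is inferred from the rule that all days in hospital count. Under those rules pre-dose days can enter ICU and hospital length of stay.

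The consequence is added noise, with no bias and no inflation of type I error. Under the assumed distributions, power falls by about 1 to 7 points with 0 to 3 pre-dose days, and by about 10 to 16 points only if about a quarter of patients have long pre-dose stays. ICU-free days are at risk, not shown to be affected.

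Priority is minor. These are secondary endpoints, analysed descriptively with nominal p-values (SAP 5.3 and 5.9), and they carry no success criterion.

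**What to change.** In SAP 4.4:

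1. Count ICU, hospital, ventilator and vasopressor days from the calendar day of dosing (Day 1) through Day 28, in line with the table titles and with the start already stated for ventilator-free and vasopressor-free days.
2. Define ICU-free days as the days from Day 1 to Day 28 on which the patient is alive and out of the ICU, so that they are not derived by subtracting ICU time from 28.
3. Report pre-dose ICU and hospital days as baseline characteristics by arm.
4. List total length of stay descriptively, which keeps it available for the health-economic use in Protocol 10.3.

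The cost is SAP wording and programming. ICU and hospital admission and discharge dates are already collected from screening on (Protocol 7.3), and the day of dosing defines Day 1. The downside is that total stay is no longer the tested measure.

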4.5 Safety Endpoints

Adverse events and clinical parameters (HR, BP, vital signs), laboratory parameters (clinical chemistry and hematology), and survival will be evaluated as safety endpoints.

5 Analysis Approaches

5.1 Preliminary and Descriptive Analyses

Descriptive analyses will be performed in order to characterize the treatment groups and to confirm that the randomization resulted in no clinically significant group differences at baseline. Baseline variables will be compared between groups using means, standard deviations, median, minimum and maximum values for continuous variables and counts and percentages for categorical variables. Although emphasis will be on clinical significance, baseline comparisons will include t-tests or Wilcoxon rank sum tests as appropriate for interval variables and chi-square or Fisher's exact tests as appropriate for nominal variables to aid in the screening for baseline differences. Similarly, changes in clinical endpoints over time will be summarized within each treatment group using summary statistics including mean and median change scores, standard deviations and ranges. Pearson or Spearman rank correlation coefficients will be used to characterize associations among variables within treatment group. For time-to-event outcomes (i.e., event-free survival), descriptive analyses will include construction of group specific Kaplan-Meier survival curves as appropriate.

5.2 Primary Endpoint

The primary efficacy comparison involves testing the following one-sided superiority hypotheses: **H₀**: $\pi_{0.50} - \pi_{\text{placebo}} \leq 0$ vs **H_a**: $\pi_{0.50} - \pi_{\text{placebo}} > 0$; where $\pi_{0.50}$ and π_{placebo} represent the true probability of freedom from durable loss of renal function at Day 28. Each probability represents the proportion of subjects on each arm expected to achieve complete recovery. These hypotheses will be tested using a one-sided type 1 error rate of $\alpha=0.05$. The null hypothesis will only be rejected if the investigational drug demonstrates superiority. An unadjusted chi-square test will be used to test this hypothesis. The corresponding two-sided type 1 error rate is $\alpha=0.10$. Therefore, the null hypothesis will be rejected if the chi-square p-value is less than 0.10. The corresponding 90% two-sided confidence interval will be provided. The lower bound of the 90% confidence interval is equivalent to the lower bound of a 1-sided 95% confidence interval. Based on the study data, it can be concluded that the true difference in success rates is at least equal to the lower bound of the 1-sided 95% confidence interval.

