9.2.10 Clinical Scores

Clinical scores/criteria components will be collected in the study. APACHE II score criteria will be determined only at screening (see Section 18.2) while SOFA score will be determined throughout the study (see Section 18.3). APACHE II will be used to determine disease severity while SOFA score will be evaluated as an inclusion criteria and as a secondary clinical endpoint. Individual parameters of the SOFA score will be collected and will also be correlated to response. All scores, except the Screening SOFA, will be calculated retrospectively. Data will be recorded in the eCRF at specified time points according to time and events, see Section 18.1.

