12.5 Synopsis of Key Statistical Approaches

12.5.1 Primary Efficacy Comparison

The primary efficacy comparison involves testing the following one-sided superiority hypotheses: **H₀: $\pi_{0.50} - \pi_{\text{placebo}} \leq 0$ vs H_a: $\pi_{0.50} - \pi_{\text{placebo}} > 0$** ; where $\pi_{0.50}$ and π_{placebo} represent the true probability of freedom from durable loss of kidney function (alive, free of dialysis, and less than a 37% loss of eGFR (measured with the MDRD formula from the patient's reference eGFR)) at Day 28. Each probability represents the proportion of subjects on each arm expected to achieve freedom from durable loss of renal function. These

hypotheses will be tested using an unadjusted chi-square test at a one-sided type 1 error rate of $\alpha=0.025$. The null hypothesis will only be rejected if the proportion of responders is larger in the active drug group compared to placebo. It is a noteworthy advantage of the sample size re-estimation approach to be used (see details below) that the conventional test statistic may be used to test the primary hypothesis and there is no need to weight subjects randomized after the sample size re-estimation differently from those randomized before the sample size re-estimation.

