12.5.2 Sample Size Justification

This trial will enroll 120 subjects who will be randomized in a ratio of 1:1 to either Reltecimod 0.50 mg/kg or placebo, each in addition to SoC. Sample size analysis was performed assuming that all patients will be evaluable for the primary endpoint using last observation carried forward (LOCF) for patients missing creatinine on Day 28. The primary efficacy hypothesis will be tested using an unadjusted χ^2 statistic with a one-sided $\alpha=0.025$ significance level. Rejection the null hypothesis will only occur if investigational drug superiority is demonstrated. Statistical power was computed for a range of expected treatment group differences supported by the results of preliminary studies. Table 6 summarizes the statistical power for a fixed sample design with a total sample size of $N=120$ (60 per group) for various assumptions regarding the success rate in the investigational arm and assuming a success probability of 0.50 among controls. This sample size results in 81.6% power if the true success rates are 75% and 50% for the investigational and placebo, respectively, a group difference of 25%.

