2.1.2 Sample Size Justification

This trial will enroll 120 subjects randomized in a 1:1 ratio to either Reltecimod 0.5 mg/kg (n=60) or placebo (n=60), both in addition to standard of care (SoC). Sample size analysis was performed assuming all patients will be evaluable for the primary endpoint due to using last observation carried forward (LOCF) for patients missing the creatinine value on Day 28. The primary efficacy hypothesis will be tested using an unadjusted χ^2 statistic with a one-sided $\alpha=0.05$ significance level. Rejection of the null hypothesis will only occur if investigational drug superiority is demonstrated. Statistical power was computed for a range of expected treatment group differences supported by the results of preliminary studies. The following table summarizes the statistical power for a total sample size of N=120 (60 per group) for various assumptions regarding the success rate in the investigational arm and assuming a success probability of 0.50 among controls. This sample size results in 89% power if the true success rates are 75% and 50% for the investigational drug and placebo, respectively, for a group difference of 25%. Power remains above 80% if the true group difference is at least 22% (Table 1).

Table 1. Computed Power			
Index	Control	AB103	Power
1	0.5	0.65	0.507
2	0.5	0.70	0.727
3	0.5	0.71	0.766
4	0.5	0.72	0.802
5	0.5	0.73	0.834
6	0.5	0.74	0.864
7	0.5	0.75	0.890

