3.10.2 Screening AKI and Screening eGFR

Screening (pre-dose) AKI will be determined by comparing screening (pre-dose) creatinine to the algorithmic determination of reference as described in Exhibit 1 based on the rules summarized in Exhibit 2.

The screening creatinine is necessary to establish baseline eGFR. However, according to the Clinical Protocol, the AKI stage used to determine eligibility into the study may be determined through urine outcome criteria. If there is any discrepancy between the algorithm and the assignment by the site as to reference creatinine then this will generate a medical review which may result in a modified baseline AKI stage different from the algorithmic determination. However, in all cases, the algorithmic determination will be used when determining eGFR. All such cases will be documented in the clinical study report. Sensitivity analyses will be conducted as needed to evaluate the impact of any modifications from the algorithmic determination in Screening AKI stage.

Exhibit 2. Algorithmic Determination of Screening (pre dose) AKI Stage	
Stage	Serum Creatinine
0	<1.5 times reference
1	1.5 to <2.0 times reference
2	≥2 to 3 times reference
3	≥ 3 times reference OR Increase in serum creatinine to ≥4 mg/dL OR Initiation of renal replacement therapy
Reference may be either algorithmically determined or independently adjudicated depending on analysis.	

Screening eGFR will be determined using the following formula.

$$\text{Screening eGFR (mL/min/1.73 m}^2\text{)} = 175 \times (\text{Screening Cr})^{-1.154} \times (\text{Age})^{-0.203} \times (0.742 \text{ if female}) \times (1.212 \text{ if African American}).$$

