5.7 Analysis of Other Covariate Effects

Covariates will be assessed for potential confounding (due to lack of perfect randomization balance) or effect modification (subgroup efficacy heterogeneity) using Mantel-Haenszel stratified analyses and/or multiple logistic regression. Covariates will include the set of variables listed above for subgroup analyses. Other baseline variables in which randomization failed to produce balance between groups will be examined in supporting analyses. Covariate effects on estimates and interactions will be assessed to see if there is evidence of efficacy heterogeneity. Results from all subgroups analyses will be considered hypothesis-generating.

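### The primary chi-square test does not use severity measured before dosing; adjusting for it could lift power from 89% to about 90–95% at the SAP's one-sided 0.05, depending on an unknown correlation

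*SAP*

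**What the plan says.** SAP 5.2 sets the primary comparison of the two Day 28 success proportions: "An unadjusted chi-square test will be used to test this hypothesis". SAP 2.1.1 and 8.1 and Protocol 12.5.1 name the same test. The SAP uses a one-sided level of 0.05 and the Protocol 0.025. SAP section 1 says the SAP governs where the two differ.

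The stated power depends on that level. SAP 2.1.2 says: "This sample size results in 89% power if the true success rates are 75% and 50% for the investigational drug and placebo, respectively". Protocol 12.5.2 gives 81.6% for the same rates and the same 120 patients.

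Severity is recorded before dosing. Screening SOFA is an eligibility criterion (Protocol 6.1, item 3) and must be scored before study drug is given. On creatinine, SAP 3.10.2 says: "The screening creatinine is necessary to establish baseline eGFR". Randomisation is stratified within site by AKI acuity and age group only (SAP 2.2).

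Covariates appear in SAP 5.7 and Protocol 12.9 as supporting checks for confounding and effect modification. The SAP 5.7 list is the subgroup list in SAP 5.6, which includes AKI stage, APACHE II at a cut of 10, and cardiovascular and respiratory failure.

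**The concern.** Success requires survival, freedom from dialysis and limited eGFR loss at Day 28. Protocol 4.1.1 itself ties organ dysfunction in sepsis to death, and AKI severity to long-term dialysis and chronic kidney disease. It is therefore reasonable to expect pre-dose organ-failure and renal measures to predict the outcome. A test that omits them carries variance that could be removed at no cost in patients. Adding only the two stratification factors would not recover this information, because neither factor measures severity.

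The second issue is chance imbalance. With 60 per arm, a standardised covariate's between-arm mean difference has a standard deviation of √(2/60) = 0.18. If that covariate correlates 0.4 with the outcome at a 50% success rate, a one-SD imbalance moves the unadjusted difference by 0.4 × 0.5 × 0.183 = 3.7 percentage points. The plan's response is to test for baseline differences and then examine the variables that look unbalanced (SAP 5.1, 5.7). That choice depends on the data and leaves the primary result unchanged.

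**Working it through.** **Inputs.** Success rates 0.50 and 0.75, 60 per arm, all patients evaluable (SAP 2.1.2); one-sided 0.05 (SAP 5.2) or 0.025 (Protocol 12.5.1). The correlation r between the baseline covariates and the outcome within arm is not in either document. It is assumed here, over 0.2 to 0.5.

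**Reproducing the stated power.** With pooled null variance and no continuity correction:

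power = Φ{ [0.25√n − z√(2 × 0.625 × 0.375)] / √(0.25 + 0.1875) }

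- One-sided 0.05, n = 60: (1.9365 − 1.645 × 0.6847) / 0.6614 = 1.225, giving 88.97% (SAP: 89%).
- One-sided 0.025, n = 60: (1.9365 − 1.960 × 0.6847) / 0.6614 = 0.899, giving 81.57% (Protocol 12.5.2: 81.6%).

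Both figures reproduce. They differ only because the levels differ.

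**Effect of adjustment.** Adjustment reduces the variance by a factor of about 1 − r², so n is replaced by 60/(1 − r²) in the same formula.

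| r | effective n per arm | power, one-sided 0.05 | power, one-sided 0.025 |
|---|---|---|---|
| 0 (as planned) | 60.0 | 89.0% | 81.6% |
| 0.2 | 62.5 | 90.1% | 83.1% |
| 0.3 | 65.9 | 91.4% | 85.1% |
| 0.4 | 71.4 | 93.2% | 87.8% |
| 0.5 | 80.0 | 95.3% | 91.2% |

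At the SAP's level the gain is about 1 to 2 points for r of 0.2–0.3, and 4 to 6 points for 0.4–0.5.

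**Simulation check.** This used 20,000 trials per setting and one normally distributed covariate, with an adjusted risk difference and robust standard error.

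- r = 0.4: adjusted power 93.0% at 0.05 and 87.8% at 0.025.
- r = 0.5: adjusted power 95.2% and 91.2%.
- r = 0: adjusted 88.7% vs chi-square 89.6% at 0.05, and 81.3% vs 81.7% at 0.025. This is the source of the cost of up to about 1 point.
- No treatment effect: the adjusted test rejected in 5.0–5.1% of trials at 0.05 and 2.4–2.5% at 0.025. The chi-square rejected in 5.3–5.6% and 2.8%.

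The simulated chi-square reached about 90% power at 0.05 because it rejects slightly more often than nominal. Against that benchmark the gain at r = 0.4 is about 3 points.

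**Two features of the SAP that affect the covariate.**

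- *Reference creatinine.* SAP 3.10.6 replaces a reference above 1.4 with the MDRD-derived value when creatinines from Day 10 onward vary by 1.5-fold. The final reference can therefore depend on post-dose data.
- *Baseline for eGFR loss.* SAP 2.1.1 and 4.1 define loss from reference eGFR, but the formula in SAP 3.10.3 uses screening eGFR. Under the MDRD exponent a 37% loss is a creatinine rise of 0.63^(−1/1.154) = 1.49-fold. Measured from screening, a patient screened at 3 times reference fails the eGFR component only at about 3 × 1.49 = 4.5 times reference. A high screening ratio would then make that component easier to pass, even if it predicts death or dialysis.

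**The case against.** An unadjusted primary test with adjusted supporting analyses is a legitimate, pre-specified choice, and nothing here shows bias or inflated type 1 error. That stands. A reader might infer that the test is invalid or that the plan disregards severity; SAP 5.6 and 5.7 contradict the second inference, since several severity measures are on the supporting list.

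A reader might also take the gain to be 82% to roughly 87–91%. That range starts from the Protocol's 0.025 test and takes the upper part of an assumed correlation range. The SAP governs, tests at 0.05 and starts from 89%.

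The higher correlations may not be reached. Under a logistic model with a normally distributed score and 50% success, r of 0.4–0.5 corresponds to an AUC of about 0.73–0.79. Entry is limited to Stage 2–3 AKI, and patients not expected to survive 28 days are excluded. Some patients qualify on urine output alone, and RRT before dosing may lower screening creatinine in severe cases. These features could all weaken the association.

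Protocol 12.5.1 also links the conventional statistic to the sample size re-estimation. Its contrast is with weighting patients by stage, not with covariate adjustment, so it does not bar the change. It is a fair reminder that the Protocol text must change too.

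Finally, not every severity measure will be complete. SAP 3.7.2 anticipates missing APACHE II components. The covariates proposed below do not use APACHE II.

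**Conclusion.** The point holds as one of efficiency and robustness. The primary test leaves out severity measured before dosing, and the supporting checks in SAP 5.7 do not alter the primary result. At one-sided 0.05 the likely gain runs from about 1 point (r = 0.2) to about 6 points (r = 0.5). At one-sided 0.025 it runs from about 2 to about 10 points. The size rests on the plan's 50% vs 75% and 60 per arm, on full evaluability, and on a correlation the documents do not supply. The contribution of the creatinine ratio cannot be judged until the reference-versus-screening definition of eGFR loss is reconciled. The change is worth making because its cost is small, but the upper end of the range should not be quoted as expected.

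**What to change.** In SAP 2.1.1, 5.2 and 8.1, and in the Protocol synopsis and 12.5.1, make the primary analysis a covariate-adjusted marginal difference in success proportions: a logistic model with standardisation and a robust standard error. Take both the one-sided p-value and the confidence interval from this estimator. SAP 5.2 and 8.1 draw a conclusion from the interval bound, and a conditional logistic p-value beside a marginal interval could disagree with it. The hypothesis on the difference in proportions is unchanged.

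Pre-specify strictly pre-dose covariates:

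- screening SOFA total, or mSOFA as the SAP's primary score (SAP 3.7.1);
- log(screening creatinine / reference creatinine), using the Exhibit 1 reference before any SAP 3.10.6 replacement.

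State which pre-dose creatinine is used for patients who began RRT before dosing, since SAP 3.10.6 excludes samples drawn close to RRT start. Reconcile SAP 3.10.3 with 2.1.1 and 4.1. Keep the unadjusted chi-square as a supporting analysis, and align the test named in SAP 2.1.2 and Protocol 12.5.2.

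**Cost.** No new data; revised wording in both documents and one model, settled before unblinding. The primary p-value becomes model-based. If the covariates are not prognostic, up to about 1 point of power is lost. The simulation above used a linear adjusted risk difference, so the chosen standardised estimator should be simulated at 60 per arm before the SAP is finalised.
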